## 5.5 Premature termination

IBSA as the Sponsor has the right to terminate the trial prematurely if there are any relevant medical or ethical concerns, or if completing the trial is no longer practicable. If such action is taken, the reasons for terminating the trial must be documented in detail. All trial subjects still under treatment at the time of termination must undergo a final examination which must be documented.

IBSA as Sponsor should submit notification of premature termination or temporary halt to IEC and CA, providing justification for the decision.

## 6 TREATMENTS

### 6.1 Investigational / Non Investigational Medicinal Product (IMP/NIMP)

STUDY MEDICATION CHARACTERISTICS	
Generic/Trade Name:	Tirosint®
Chemical Name:	L-3,3',5,5'-tetraiodothyronine sodium salt [levothyroxine sodium]
Structural Formula and Molecular Weight (MW):	
Name of Manufacturer/Marketing Authorization Holder (MAH):	Empirical formula: C 15 H 10 I 4 N NaO 4 • H 2 O  MW: 798.86 g/mol (anhydrous)  Manufactured by: 

Formulation:	Distributed by:  IBSA Pharma Inc Parsippany, NJ 07054, USA
Strength:	capsule  13, 25, 50, 75, 88, 100, 112, 125, 137, 150, 175, 200 mcg
Dose regimen:	once daily
Route of administration:	oral
Storage Conditions:	Store at 25°C (77°F); excursions permitted to 15°-30°C (59-86°F) [See USP Controlled Room Temperature]. TIROSINT capsules should be protected from heat, light and moisture

## 6.2 Dosage and administration

The following strengths of Tirosint® (levothyroxine sodium) capsules are available by prescription on the market: 13, 25, 50, 75, 88, 100, 112, 125, 137, 150 mcg. The 175 and 200 mcg strengths have been recently authorized, but may not be supplied until they will become available on the market. The strengths necessary to obtain the dosage schedule between 88 and 250 mcg/day will be provided. Where the strength is not available, doses higher than 150 mcg will be obtained by combining different strengths (e.g. 100+75 mcg capsules =175 mcg, 100+100 mcg capsules =200 mcg, 125+100 mcg capsules =225 mcg, 150+100 mcg capsules =250 mcg). Additional or intermediate daily dosages may be obtained by using also the lowest strengths, between 13 and 50 mcg.

Different batches may be provided during the course of the study.

At screening the Investigator will accurately report the information regarding LT4 product and dose, as well as PPI product and dose with which the patient is on therapy in the Case Report Form (CRF).

During the first 4 to 6 weeks of the study (run-in phase), patients will continue taking their levothyroxine and PPI medications as per prescription, at their current dose.

Upon baseline visit and inclusion, patients will be switched to Tirosint® capsules at the same dose under which he/she is currently being treated and will remain on Tirosint® for 12±1 weeks. Each patient will be dispensed 2 boxes (60 capsules) of the appropriate Tirosint® strength at Visit 2 and 2 boxes (60 capsules) of the appropriate Tirosint® strength at Visit 3. These should allow treatment for 6 weeks plus a reserve in case of delay of the subsequent visit. Additional boxes may be dispensed in case the dosing schedule requires combination of several strengths (for instance, in case of daily dose of 200 mcg, 4 boxes of 100 mcg will be dispensed). The Investigator will make sure that the patient is given enough supplies for treatment up to the next visit.

At the same time, patients will continue their regular intake of Rx PPI, throughout the whole study duration, according to prescription.

Tirosint® will be taken as a single daily dose in the morning, on an empty stomach, one-half to one hour before breakfast, according to labelling. All subjects will separate their LT4 by at least 4 hours from any drug known to interfere with LT4 absorption (e.g. iron and calcium supplements, see section 6.5) and by at least 1 hour from foods that are known to interfere with LT4 absorption.

The patients will continue intake of PPI according to their individual prescription and habits.

Patients will remain on their pre-screening dose (both for LT4 and for PPI) throughout the whole study duration.

No LT4 dose adjustments will be allowed during the whole study, unless TSH levels > 10 or < 0.01 mIU/L are measured, which require immediate dose adjustment of LT4. In particular:

- If TSH levels > 10 or < 0.01 mIU/L are measured during the baseline visit the subject will drop-out, because pre- and post-switch comparisons at the same dose would not be possible.
- If TSH levels > 10 or < 0.01 mIU/L are measured during control visits (interim or unforeseen), the dose will be adjusted and the subject will remain in the study. To the purpose of the efficacy evaluation in such cases reference is made to section 11.3.

The Investigator can adjust the LT4 dose for a patient with TSH levels < 10 or ≥ 0.01 mIU/L, if this is considered necessary for the safety of a patient. The reason should be appropriately documented.

Changes in the dose of PPI are acceptable during the study provided that the dose remains ≥ 20 mg/day for omeprazole, esomeprazole and rabeprazole, ≥ 15 mg/day for lansoprazole, ≥ 30 mg/day for dexlansoprazole, and ≥ 40 mg/day for pantoprazole. If the newly prescribed dose falls outside this range or if the therapy with PPI is interrupted, the subject will drop out of the study.

Any changes will be described in the CRF.

### **6.3 Packaging and labeling**

Tirosint® will be supplied in its original packaging material, as boxes of 30 capsules, consisting of 3 blisters with 10 capsules each. The dosage strength on each box is clearly identified in several locations, and is associated with a distinct colour. The colour of the circles on the blister is the same colour as on the box. Each blister pack contains 10 capsules placed in individual cavities labeled with the dosage strength, the product name (TIROSINT), and an abbreviation for the day of the week on which the capsule is taken.

The individual cavities containing the drug should not be separated from the intact blister as important information may be lost (i.e., manufacturer/distributor names, distributor contact phone number, lot number, and expiration date), and the individual capsules should not be removed from blister packaging until ready to use.

Because it is not possible to know in advance which strength of Tirosint® will be administered to each patient, no individual subject supplies will be prepared.

Study specific information will be reported in an additional label without covering the original information.

Study-specific labeling of Tirosint® will be performed by IBSA Institut Biochimique SA, Switzerland, in accordance with Good Manufacturing Practices (GMPs) requirements, and with local regulations and will report at least the following information:

- Sponsor's name and contact information
- Study N°
- Subject N° (blank)
- Date of dispensing (blank)
- "For clinical trial use only."

At the time of dispensing, the Investigator or designee will be required to write on the label of the box of the IMP the Subject N. and the date of dispensing.

Investigators' name, address and telephone number (main contact information on the product and clinical trial) will be provided separately on a Patient's Card, that the Investigator or designee will give to the patients at the time of dispensing, with the instruction to keep it in their possession at all times.

Labels will have a tear-off part to allow for proper tracking of dispensing.

#### **6.4 Storage and accountability**

After receipt of the drug supplies (IMP), the Clinical Investigator, his/her deputy or the Pharmacist will conduct an inventory and subsequently fill-in and sign the Drug Receipt Form. Drug inventory and drug accountability records will be kept by the Investigator, his/her deputy or the Pharmacist.

Any particular storage condition will be rigorously followed (see section 6.1).

The Investigator and/or Pharmacist will keep study drugs in a pharmacy or a locked and secure storage facility, accessible only to those individuals authorized by the Investigator and/or Pharmacist himself.

At the conclusion of the study, a final study drug inventory for IMP will be performed and any unused drug will be returned together with a Drug Return Form accurately filled-in and signed by the Clinical Investigator or his/her deputy or by the Pharmacist. If any supplies are missing, this must be indicated together with an explanation for the discrepancy.

At Visit 2, the Investigator will select the appropriate strength of IMP to be provided to the patient, he/she will appropriately fill in the Drug Accountability Form with Subject N. and dispensing date, write the Subject N. and the dispensing date on the dispensed boxes, and stick the tear-off parts of the labels in the appropriate space of the Drug Accountability Form.

---

 Please notice that the terms Subject N. and Patient N. are considered equivalent.

The Investigator will make sure that the patient is given enough supplies for treatment up to the next visit.

The patients will be instructed to bring back the empty boxes and blisters, as well as the partially used and/or unused boxes and blisters at the next visit. Upon return, the Investigator will record the number of units used and unused and the date of return on the Drug Accountability Form.

At the last visit all the boxes and blisters will have to be collected, being them either used, unused or partially used.

Returned boxes (either used, partially used or unused) will not be discarded, but stored by the Investigator or Pharmacist for drug accountability check purposes, separately from the unused supplies. Boxes that have been dispensed to a patient and are returned unused cannot be re-dispensed to another patient, but will be stored by the Investigator or Pharmacist together with the used boxes.

## 6.5 Concomitant medications and study restrictions

All concomitant medications (prescription and OTC) taken in the time frame from screening to the end of the study will be recorded in the Concomitant Medication section of the CRF. Multivitamins and other supplements will also be recorded.

Many drugs can affect thyroid hormone pharmacokinetics and may alter the therapeutic response to LT4 (IBSA Pharma Inc 2018). Unless otherwise specified, **the following medications will be forbidden throughout the study period** (from screening to final visit). If administration of such medication becomes necessary during the course of the study, subject withdrawal or continuation should be discussed between the Investigator and the Sponsor.

Thyroid hormones other than those involved in the study, e.g. triiodothyronine (LT3), LT4+LT3 combinations or desiccated thyroid extracts.

Drugs That May Alter Hepatic Metabolism of T4 (Hypothyroidism):

- Phenobarbital
- Rifampin

Potential impact: Stimulation of hepatic microsomal drug-metabolizing enzyme activity may cause increased hepatic degradation of levothyroxine, resulting in increased levothyroxine requirements.

Drugs That May decrease conversion of T4 to T3:

- Beta-adrenergic antagonists (e.g., Propranolol > 160 mg/day)
- Glucocorticoids (e.g., Dexamethasone  $\geq$  4 mg/day)
- Other: Amiodarone

Drugs That May Alter T4 and Triiodothyronine (T3) Serum Transport Without Affecting Free Thyroxine (FT4) Concentration (Euthyroidism):

- Clofibrate (Atromid-S)
- Heroin / Methadone
- 5-Fluorouracil
- Mitotane
- Tamoxifen
- Steroids (estrogen-containing oral contraceptives, oral estrogens, androgens / anabolic steroids, glucocorticoids)
- Asparaginase
- Slow-Release Nicotinic Acid
- Salicylates (> 2 g/day)
- Other drugs (Carbamazepine, Furosemide > 80 mg IV, Heparin)
- Hydantoins (e.g. phenytoin)
- Non-Steroidal Anti-inflammatory Drugs (Fenamates)

Drugs that may decrease T4 absorption, which may result in hypothyroidism:

- Antacids (Aluminum & Magnesium Hydroxides, Simethicone)
- Sucralfate (Carafate)
- Orlistat (Alli, Xenical)

Concurrent use may reduce the efficacy of levothyroxine by binding and delaying or preventing absorption, potentially resulting in hypothyroidism.

---

 Oral contraceptives, estrogen/progestogen replacement therapy and testosterone replacement, as well as glucocorticoids are allowed if at stable doses throughout the entire study duration (from screening to final visit).

### Antidepressant Therapy

Concurrent use of tricyclic (e.g., amitriptyline) or tetracyclic (e.g., maprotiline) antidepressants and levothyroxine may increase the therapeutic and toxic effects of both drugs, possibly due to increased receptor sensitivity to catecholamines. Toxic effects may include increased risk of cardiac arrhythmias and central nervous system stimulation. Levothyroxine may accelerate the onset of action of tricyclics. Administration of sertraline in patients stabilized on levothyroxine may result in increased levothyroxine requirements.

### Tyrosine-Kinase Inhibitors:

Concurrent use of tyrosine-kinase inhibitors such as imatinib may cause hypothyroidism.

### **Levothyroxine should be administered at least 4 hours apart from these agents:**

- Calcium Carbonate
- Ferrous Sulfate
- Bile Acid Sequestrants (Colesevelam, Cholestyramine, Colestipol)
- Ion Exchange Resins (Kayexalate, Sevelamer)

### **Caution should be considered in the following cases:**

- **Antidiabetic Therapy:** Addition of levothyroxine therapy in patients with diabetes mellitus may worsen glycemic control and result in increased antidiabetic agent or insulin requirements. Carefully monitor glycemic control, upon switch to Tirosint.
- **Oral Anticoagulants:** levothyroxine increases the response to oral anticoagulant therapy. Therefore, a decrease in the dose of anticoagulant may be warranted with correction of the hypothyroid state or when the levothyroxine dose is increased. Closely monitor coagulation tests to permit appropriate and timely dosage adjustments upon switch to Tirosint.
- **Digitalis Glycosides:** levothyroxine may reduce the therapeutic effects of digitalis glycosides. Serum digitalis glycoside levels may decrease when a hypothyroid patient becomes euthyroid, necessitating an increase in the dose of digitalis glycosides.
- **Ketamine:** Concurrent use of ketamine and levothyroxine may produce marked hypertension and tachycardia. Closely monitor blood pressure and heart rate in these patients.

- **Sympathomimetics:** Concurrent use of sympathomimetics and levothyroxine may increase the effects of sympathomimetics or thyroid hormone. Thyroid hormones may increase the risk of coronary insufficiency when sympathomimetic agents are administered to patients with coronary artery disease.

## **Foods**

Consumption of certain foods may affect levothyroxine absorption thereby necessitating adjustments in dosing. Soy and soy derivatives, cotton seed meal, walnuts, and dietary fiber may bind and decrease the absorption of levothyroxine sodium from the gastrointestinal tract. Grapefruit juice may delay the absorption of levothyroxine and reduce its bioavailability. Regular consumption of this food is therefore an exclusion criterion and it is prohibited during the whole study period (from screening to last visit). Occasional consumption is allowed.

## **Biotin**

Biotin has been reported to interfere with some immunoassays using a streptavidin-biotin complex. In the frame of the laboratory tests performed in the present study, the TSH assay (primary parameter of evaluation) is not using a streptavidin-biotin complex and is therefore not affected by high levels of circulating biotin. FT4 assay is negligibly affected (2%) by high levels of circulating biotin. SHBG is affected by high levels of circulating biotin. For this reason, information on the use of biotin should be collected in the CRF and patients should be advised to possibly interrupt biotin intake for 2 days before the visits.

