### 7.2 Screening/Inclusion

#### *Visit 1 - Day -28/-42 (Screening Visit)*

The screening procedures (Visit 1) will be performed between 4 and 6 weeks prior to inclusion.

Patients will be screened by endocrinologists.

Subjects should come to the clinical center holding their morning dose of LT4 and possibly bringing with them the box of the LT4 and PPI that they are on therapy with for a visual check by the Investigator. They will be asked to sign the Informed Consent Forms before the start of any screening procedures.

The screening visit will include:

- informed consent;
- demography;
- medical and medication history;
- general physical examination (including neck exam, cardiac exam, and respiratory exam);
- body weight (BW), height;
- vital signs (blood pressure [BP], heart rate [HR]);
- check of inclusion/exclusion criteria;
- blood sampling for thyroid function tests (TSH, FT4, FT3, TT3);

---

 The date of the informed consent signature may also precede the date of the screening visit.

- urine pregnancy test (in female subjects of childbearing potential);
- diary dispensing;
- instruction of the patient on how to complete the diary and how to comply with the study requirements (i.e. drugs intake, study restrictions, etc.).

The screened subjects will receive consecutively a Subject N. starting from 001 and preceded by a two-digit code identifying the center (where 01 = [REDACTED]). Should additional centers be involved, these will be identified as 02, 03, 04, etc.) (i.e. 01-001, 01-002, etc. and 02-001, 02-002, etc.), that they will retain from the first Screening Visit until the Final Visit.

Clinical signs/symptoms of hypothyroidism or hyperthyroidism (e.g. palpitations) reported by the patient at the screening visit, if clinically significant, will have to be recorded as medical history in the CRF.

The current LT4 product and dose, as well as the current PPI product and dose will be accurately recorded in the CRF, possibly checking with the medication box/bottle if the patient has brought them with him/her.

Subjects complying with inclusion/exclusion criteria will enter a run-in period, during which they will remain on their current dose of LT4 tablets and will keep taking their PPI as prescribed. Patients will have to fill in a diary reporting the daily intake of LT4 and PPI.

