### *11.3.3 Missing data*

Cases of withdrawal from the study, for any reasons, after inclusion will not be replaced. However, the withdrawn cases will be analyzed in the ITT analysis.

TSH, FT4, TT4, FT3, TT3, CPK, SHBG, ferritin, ACE level, and lipid panel values recorded after changes in LT4 dose will not be considered for the statistical analysis.

For analyses that require complete patient data, missing values during the treatment period will be replaced, for all primary and secondary variables, with the Last Observation Carried Forward (LOCF) technique. Imputed values will be included in the analysis set(s), but will not change the original clinical database. Sensitivity analyses based on other imputation methods (e.g. Basal Observation Carried Forward [BOCF], maximum-likelihood based method or others) may also be conducted, and will be fully described in the Statistical Analysis Plan.

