#### 7.1.2 Secondary efficacy variables

The secondary efficacy variables are the serum levels of FT4, TT4, FT3, TT3, CPK, SHBG, ferritin, ACE level, and lipid panel; and the LT4 dose adjustment.

Serum levels of FT4, FT3 and TT3 will be measured at screening visit(s), at baseline, halfway through the treatment period and at the final visit. In addition, serum levels of TT4, CPK, SHBG, ferritin, ACE level, and lipid panel (TC, HDL-C, LDL-C, VLDL-C, TG) will be measured at baseline and at the end of the 12-week treatment period (Final visit).

The change in serum levels of TSH, FT4, FT3, TT3 at Visit 3 vs baseline will also be analysed as secondary efficacy endpoint.

The serum levels of TSH, FT4, TT4, FT3, TT3, CPK, SHBG, ferritin, ACE level, and lipid panel recorded after changes in LT4 dose will not be considered for the analysis.

LT4 dose adjustment will be evaluated both in terms of number of patients requiring changes in daily dose during the treatment period and as mean change in daily LT4 dose at the end of the treatment period versus baseline.

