##### 9.4.2 Secondary efficacy analysis

- Serum levels of FT4, FT3, TT4, TT3, CPK, SHBG, ferritin, ACE level, and lipid panel (TC, HDL-C, LDL-C, VLDL-C, TG) at the end of each 12-week treatment period vs baseline

The secondary efficacy endpoints are the changes in serum levels of FT4, FT3, TT4, TT3, CPK, SHBG, ferritin, ACE level, and lipid panel (TC, HDL-C, LDL-C, VLDL-C, TG) at the end of each 12-week treatment period with Tirosint® capsules vs baseline.

Mixed model ANCOVA repeated measures models will be used to test differences in means of serum levels of FT4, FT3, TT4, TT3, CPK, SHBG, ferritin, ACE level, at Visit 4 vs baseline visit. As covariates will be considered the following baseline variables: Age, Sex, BMI and the prescribed Tirosint® dosage (dose/Kg). Unstructured covariance structure will be used (If a different type of covariance structure will be used details will be provided).

Normal distributions for each serum level data will be tested with Shapiro Wilks. If data results not to be distributed as a normal distribution the following methods will be applied:

- Data will be log transformed and analyzed with the ANCOVA repeated measures models described above.

- The change in serum levels of TSH, FT4, FT3, TT3 at Visit 3 vs baseline

Mixed model ANCOVA repeated measures models will be used to test differences in means of serum levels of TSH, FT4, FT3, and TT3 at Visit 3 vs baseline visit. As covariates will be considered the following baseline variables: Age, Sex, BMI and the prescribed Tirosint® dosage (dose/Kg). Unstructured covariance structure will be used (If a different type of covariance structure will be used details will be provided).

Normal distributions for each serum level data will be tested with Shapiro Wilks. If data results not to be distributed as a normal distribution the following methods will be applied:

- Data will be log transformed and analyzed with the ANCOVA repeated measures models described above.

The serum levels of TSH, FT4, FT3, TT4, TT3, CPK, SHBG, ferritin, ACE level, and lipid panel at each time point will also be summarized as continuous variables.

- LT4 dose adjustment

Frequencies and percentages of patients requiring changes in LT4 daily dose during the treatment period will be provided.

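### The protocol says biotin affects the SHBG assay and has its use recorded, but the SAP tests the SHBG change with no rule for biotin-exposed samples

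*Protocol*

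**What the plan says.** The Biotin paragraph of protocol 6.5 treats the assays one by one. It calls the TSH assay unaffected and the FT4 assay negligibly affected (2%). For SHBG it says "SHBG is affected by high levels of circulating biotin". It gives neither the direction nor the size of that effect.

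Two measures follow. First, "information on the use of biotin should be collected in the CRF", which fits the general rule in 6.5 that "Multivitamins and other supplements will also be recorded". Second, "patients should be advised to possibly interrupt biotin intake for 2 days before the visits". The second is advice, not a requirement. Biotin is not among the forbidden medications in 6.5 or the exclusion criteria in 5.3.

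SHBG is named in the secondary objective (protocol 3.2) and tested at Visit 4 against baseline. SAP 9.4.2 states: "Mixed model ANCOVA repeated measures models will be used to test differences in means of serum levels of FT4, FT3, TT4, TT3, CPK, SHBG". The covariates are age, sex, BMI and dose per kg.

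The only rule that removes an SHBG value concerns LT4 dose changes. Protocol 11.3.3 has "SHBG, ferritin, ACE level, and lipid panel values recorded after changes in LT4 dose will not be considered for the statistical analysis", and SAP 7.1.2 has "SHBG, ferritin, ACE level, and lipid panel recorded after changes in LT4 dose will not be considered for the analysis". The SAP does not mention biotin.

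**The concern.** The protocol identifies a measurement problem with one named endpoint and collects the information needed to deal with it. The analysis plan then makes no link between the two. Values that the protocol itself treats as open to interference enter the SHBG model on the same footing as all others.

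The design gives no protection. Under protocol section 4, each patient's baseline on standard therapy is the only control. Interference that is the same at both visits largely cancels in the change. Interference at one visit only goes straight into the change, and no comparison arm shares it. Because stopping biotin is optional, a patient may stop before one visit and not before the other. What is at stake is the reading of SHBG, one of the biochemical markers by which the switch from tablets to capsules is judged.

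**Working it through.** **Plan's own figure.** The documents give no figure for biotin. The only design calculation is for TSH (48 patients, difference 0.7, SD of differences 1.9, two-sided 0.05). It reproduces: the noncentral t gives 70.5% against the stated 70%. It does not bear on SHBG.

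**Inputs**
- Completers: 45 (SAP 4.1).
- Share of biotin users, size and direction of interference, SD of SHBG change: not given. All are assumed below.

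**Shift in the mean.** Let k be the net number of patients exposed at Visit 4 but not at Visit 2, after patients discordant in the opposite direction are subtracted. Let f be the proportional error in the exposed value. With no true change, the spurious change in geometric mean SHBG is

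(1 + f)^(k/45) − 1.

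Example: k = 5, f = −0.50 gives 0.50^(5/45) − 1 = −7.4%.

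| Net discordant k | Share of 45 | f = −10% | f = −30% | f = −50% |
|---|---|---|---|---|
| 0 | 0% | 0 | 0 | 0 |
| 2 | 4% | −0.5% | −1.6% | −3.0% |
| 5 | 11% | −1.2% | −3.9% | −7.4% |
| 9 | 20% | −2.1% | −6.9% | −12.9% |

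Interference upward reverses the sign; for k = 5, errors of +10%, +30% and +50% give +1.1%, +3.0% and +4.6%. Exposure at Visit 2 instead of Visit 4 also reverses the sign.

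**False-positive rate.** This was simulated with 45 patients, no true change, and a two-sided 5% one-sample t-test on the log change, assuming an SD of log change of 0.15. It is a simplification of the SAP model, which log-transforms only if normality is rejected.

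| k | f = −10% | f = −30% | f = −50% |
|---|---|---|---|
| 0 | 5% | 5% | 5% |
| 2 | 5% | 7% | 8% |
| 5 | 8% | 24% | 45% |
| 9 | 14% | 66% | 97% |

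The assumed SD matters. For k = 5 and f = −30%, the rate is 36% with SD 0.10 and 17% with SD 0.20.

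**Reading.** One or two net discordant patients do little. A misleading SHBG result needs several, mostly in one direction, with sizeable interference.

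**The case against.** The strongest reply is that nothing in the documents shows that the problem occurred. The protocol's warning concerns high circulating levels, and it does not say that ordinary intake distorts SHBG. The same advice applies before both visits, so patients discordant in opposite directions may offset each other. Recorded biotin would appear in the concomitant-medication tables (SAP 7.3), and data reliability is discussed case by case before analysis (protocol 11.3.4, SAP 6.6). The endpoint is one of many secondary laboratory variables in what protocol 2.2 calls a pilot study.

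Most of this stands as a limit on size. It does not close the gap. A medication table does not connect exposure to an SHBG value, and declining optional advice is not clearly a deviation.

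Three stronger readings are tempting, and the documents do not support them:

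- **Every SHBG value is kept.** This is wrong, because values after an LT4 dose change are dropped.
- **Patients enrolled before June 2018 had no advice, so their results are biased.** The document history places the biotin request in version 5.0 (15 June 2018), and the first visit was expected in January 2017. No actual enrolment dates or counts are given, nor any record of what sites told patients. Having no advice at either visit would not in itself make a pair discordant. Only patients whose Visit 2 to Visit 4 interval spanned the change could be made so by it.
- **FT3, TT3, TT4 and ferritin are also contaminated.** Protocol 6.5 is silent on these assays, and silence shows nothing either way.

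Feasibility is a fair challenge. The diary does not cover biotin: "Patients will have to fill in a diary reporting the daily intake of LT4 and PPI". SAP section 8 imputes missing medication days to the start or end of the month. A 2-day window may therefore not be recoverable for every patient.

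**Conclusion.** The gap is real: the protocol names an interference with SHBG and collects exposure data because of it, and the SAP makes no use of those data in the SHBG analysis. This much rests on the text alone.

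The size is unknown. A spurious change requires biotin exposure to differ between Visit 2 and Visit 4 in a net direction, at levels high enough to disturb the assay. The floor is zero. The shifts and false-positive rates above show what could happen under assumed inputs; a reader might take the larger entries as the expected error, but no documented figure supports that.

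The point is established for SHBG only. By the protocol's own statement it does not touch the primary TSH endpoint and hardly touches FT4. It is worth correcting because the correction is cheap, not because the main conclusion of the trial is threatened.

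**What to change.** Add to SAP 9.4.2 a further run of the SHBG model:

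1. Leave out the whole Visit 2–Visit 4 pair of any patient whose CRF shows biotin intake within 2 days before either visit.
2. Where the 2-day window cannot be resolved, treat biotin recorded as ongoing at the visit, with no documented stop, as exposure.
3. Do not fill these pairs by LOCF. SHBG is measured only at Visits 2 and 4, so carrying forward would put the Visit 2 value in place of an excluded Visit 4 value and force a change of zero.
4. Report the result beside the all-values result, with the number of pairs removed.

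Ask the central laboratory whether the FT3, TT3, TT4 and ferritin assays are affected, and apply the same rule only to those confirmed.

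The change belongs in the SAP. SAP 4.1 records that the study has already been terminated, so rewording the protocol's advice would alter no data.

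Cost: a short SAP paragraph, one laboratory query, one extra model run and a few lost SHBG pairs. If few patients took biotin, the two results will nearly agree, and that supports the SHBG finding.
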